1. BACKGROUND AND RATIONALE

Stress dramatically impacts people's lives, influencing how individuals think, behave and experience emotions (Aldwin, 2007; Lazarus & Folkman, 1984). Furthermore, stress is one of the major culprits in the development of pathologies such as depression and chronic anxiety (Yang et al., 2015). According to 'The Ipsos survey for World Mental Health Day' mental health has now become the primary concern for both Singaporeans and individuals worldwide when asked about the most significant healthcare issues in their respective countries. The top health concern among Singaporeans is mental health, with nearly half (46%) identifying it as the most pressing health issue in the country today, followed by cancer (38%) and stress (35%). The far-reaching consequences of this stress epidemic extend beyond personal well-being, impacting both the economic and healthcare sectors. Indeed, the symptoms of depression and anxiety are accountable for a substantial loss of 2.9% of Singapore's GDP (Chodavadia et al., 2023). To proactively address the potential health repercussions linked to chronic stress, the development of stress reduction interventions becomes an imperative undertaking.

Among these, mindfulness stands out. Defined by Jon Kabat-Zinn (2003, 2006) as 'paying attention in a particular way: On purpose, in the present moment, and nonjudgmentally,' mindfulness offers a way to alleviate stress with interventions that can be self-administered. These approaches encompass different aspects such as fostering a non-judgmental attitude and embracing inner experiences, consistent with other mindfulness methods. However, compared to traditional protocols (such as Mindfulness Based Stress Reduction; MBSR; Kabat-Zinn, 2003), these interventions 1) do not require the presence of an instructor, 2) are always available, and 3) are relatively cheap (Spijkerman et al., 2016). As these interventions show promise in effectively managing stress for a significant portion of the population, given their scalability, it is imperative to gain a thorough understanding of their efficacy.

2. AIMS AND HYPOTHESES

This pilot study seeks to assess the impact of a three-day mindfulness intervention on the stress response of Singaporean adults aged 21 or more. Specifically, we will anticipate a modest yet discernible reduction in stress levels compared to a control condition, represented by a sham meditation group.

In addition to evaluating the effectiveness of the decentralized mindfulness intervention and its comparison with the sham meditation control group, this study will also incorporate an assessment of the credibility and usability of the survey-based methodology employed.

Participants' feedback regarding the clarity of survey instructions, ease of navigation, and overall user experience will be solicited through post-intervention questionnaires. Insights gleaned from participants' perspectives will inform refinements to the methodology, ultimately optimizing its utility for a fully decentralized study on mindfulness on a larger scale.

3. EXPECTED RISKS AND BENEFITS

The study's primary advantage lies in providing participants from the intervention group with access to a 3-day mindfulness intervention, potentially contributing to stress reduction. Although the study poses no significant risks for participants, a meta-analysis reviewed 36 randomized controlled trials (RCTs) from 7931 search records, including 25 that used Mindfulness-Based Stress Reduction (MBSR) and 11 that used Mindfulness-Based Cognitive Therapy (MBCT), and found that both the mindfulness intervention group and the control group reported 19 adverse events each, accounting for 1% and 0.9% of participants, respectively. In the MBSR group, which had 1231 participants, only three studies (12.0%) reported six adverse events (0.49%) related to the intervention, with no significant adverse events recorded (Wong et al., 2018). In conclusion very few adverse events were reported in RCTs involving MBSR/MBCT, making mindfulness-based interventions generally considered to be safe.

Data privacy

The collection of health-related information via smartphone applications may pose a minor privacy risk in the event of device compromise or data transmission breaches. To mitigate these risks, all participant data will be encrypted to ensure the secure flow and storage of information.

Only essential contact information, including phone numbers and email addresses, will be collected. Phone numbers will primarily be used to reimburse participants and to prevent duplicate survey submissions. At a designated point in the study, participants will be required to send a CSV file to the study coordinator. Upon receipt, the CSV file will be downloaded, and the associated email will be promptly deleted. This information will not be retained. Additionally, all phone numbers will be permanently deleted once data collection is complete.

4. STUDY POPULATION

4.1. Number and nature of participants to be enrolled.

Being this a pilot study, the target recruitment is set at 60 participants, aged 21 or older.

4.2. Criteria for Recruitment and Recruitment Process.

Participants will be recruited from the general Singaporean community. To streamline the recruitment process, we will utilize the broad reach of social media platforms, including Facebook, Instagram, and X (formerly Twitter), where we will post a detailed description of the study.

Interested individuals will be directed to complete an online form (e.g. FormSG, Microsoft Forms etc), where they will answer questions related to the inclusion and exclusion criteria and provide a phone number for potential follow-up by the study coordinator. Those who meet the inclusion criteria will be contacted via phone (e.g. WhatsApp) by the study coordinator, who will guide them through the subsequent steps outlined in the procedure section.

The study coordinator will review the form responses daily and will close the link once 60 participants have been confirmed as meeting the inclusion criteria.

The trial involves a brief, fully anonymized online survey conducted over three consecutive days, with Day 1 and Day 3, requiring a commitment of approximately 35 minutes and Day 2 a commitment of 25 minutes. Given the study's minimal risk, non-invasive nature, and the absence of medication administration, we will seek an exemption from the requirement for traditional written consent.

To further enhance recruitment, we will collaborate with ASTAR's administrative team to notify potential participants in their database who have consented to receive research-related communications. Information about the study will also be shared through ASTAR's internal channels, in full compliance with digital platform regulations.

4.3. Inclusion criteria

Participants meeting all the following criteria will be included in the study:

- Aged at least 21.
- Possess a smartphone that can run the study applications with an internet access.
- Fluent in the English language to understand the audio tracks, the study instructions and study assessments.
- Sufficient vision and hearing to complete study procedures
- Willing to commit to the study procedures

All inclusion criteria will be assessed based on self-reported information during screening.

4.4. Exclusion Criteria

Participants meeting one or more of the following criteria below will not be included in the study:

- Past (< 6 months prior to the study) or current major neurological and psychiatric disease.
- Having meditated in the 6 months preceding the experiment.

- Participants who are currently taking psychoactive medications, including antidepressants, anxiolytics, hypnotics, and stimulants, or who have used these medications in the past week.
- Members of the research team or their immediate family members. An immediate family member is defined as spouse, parent, child, or sibling, whether biological or legally adopted.

All exclusion criteria will be assessed based on self-reported information during screening.

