5.4 Study procedures

Participants expressing interest will first complete an initial online screening form (e.g., via FormSG or Microsoft Forms), containing non-sensitive questions to assess eligibility based on study criteria such as English proficiency, age, meditation experience, vision and hearing capabilities, willingness to commit to the study procedures, and any relation to A*STAR research team members. Participants will also provide their phone number, which will be used to notify them of their eligibility status. The phone number will be retained until the end of data collection to prevent repeat participation, facilitate the delivery of study materials, and ensure compensation via e-vouchers. The study coordinator will check whether a mobile number has been previously used and stop participants if a duplicate number is detected.

Once the study coordinator reviews the responses daily, eligible participants (i.e., those meeting inclusion and exclusion criteria and those who provided a phone number not previously entered in the survey), will receive a standardized text

message (e.g., via WhatsApp) confirming their preliminary eligibility. For ineligible participants, their collected data will be discarded. If eligible, participants will be informed that the study will begin within three weeks. Upon the recruitment of the 20th participant or at the end of the third week, the coordinator will notify the cohort, instructing them to start the study within two days. The study will consist of three cohorts of 20 participants each. If fewer than 60 participants are recruited after the third cohort, an additional cohort will be organized to reach the target number.

At this point, participants will receive a message containing the following: a link to access the Qualtrics survey, an access code (which serves as an anonymous identifier), and a link to instructions for downloading the 'Camera Heart Rate Variability' app, used for heart rate variability (HRV) measurement. The instructions will detail how to take measurements and submit the generated HRV.csv data files to the study team. Participants will also receive a code to download the app for free. They will be advised to complete the survey each day at the same time, between 9 am and 9 pm.

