The Qualtrics link contains the written informed consent form and the actual experiment. Participants will be able to review all relevant information about the study and either accept or decline to participate. If they do not provide consent, they will be opted out of the study. If consent is provided, participants will proceed to the second screening, which involves answering additional questions about their use of concomitant medication. If they meet the criteria for this stage, they will proceed to answer questions about any neurological or psychiatric conditions. If any of the screening criteria are not satisfied at any point, the study will automatically terminate. Once consent and second screening are complete, participants will then be instructed to move to a quiet environment where they will not be disturbed for the next 35 minutes. They will be asked to download the 'Camera Heart Rate Variability' app and take an initial HRV measurement for testing purposes. Participants will then submit the generated CSV file to the study coordinator via WhatsApp and self-report their rMSSD values in the Qualtrics survey. Participants are instructed to label their CSV files using their anonymous identifier provided by the study coordinator via WhatsApp at the start. Afterward, they will complete a series of questionnaires, including the 20-item IPIP scale, the RS-14, the FFMQ, and various demographic questions such as age, gender, ethnicity, smartphone type used during the experiment, and its operating system (iOS or Android) and version. Pre-intervention assessments of STAI-6, EMA will also be conducted. They will then use the 'Camera Heart Rate Variability' app to measure HRV, submit the generated CSV file to the study coordinator, and self-report their rMSSD values in the Qualtrics survey, as outlined in the instructions.

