Participants who express interest in the study will first complete an initial screening, where non-sensitive questions will be asked to assess their English proficiency, age, meditation experience, vision and hearing capabilities, willingness to commit to study procedures, and any relation to A*STAR research team members. If participants do not meet the inclusion/exclusion criteria at this stage, their responses will be promptly disposed of to ensure anonymity. If they qualify, they will be sent a link to the Qualtrics platform, which will contain the written informed consent form and the actual experiment.

Given that the study poses minimal risk to participants, does not involve the use of medication, and is not expected to result in any incidental findings, we will implement a written informed consent process. Participants will be able to review all relevant information about the study and provide their consent through the online survey used for the experiment. A study coordinator and witness will not be present during the consent process. If participants choose not to consent, they will be opted out of the study. Those who do provide consent will be asked additional questions regarding their use of concomitant medication. If the participant satisfies this inclusion criteria he will pass at the next window of the survey where he will answer a question related to neurological or psychiatric conditions. If any screening criteria are not satisfied, the study will automatically terminate at that point.

As part of standard ethical procedures, participants will provide their consent by completing a written form administered through the online survey platform. We will collect participants' phone numbers to facilitate compensation and to prevent multiple survey submissions. All phone numbers will be deleted at the end of the trial.

Although participants will email the study coordinator with the generated CSV file, their email addresses will not be collected, and once the CSV file is downloaded, the email will be permanently deleted. All other data collected will be de-identified to protect participants' anonymity.

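### The six-month no-meditation rule runs to the start of the experiment, but meditation is asked only on the initial form, up to 23 days earlier, so practice begun while waiting would go undetected

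*Combined protocol and SAP*

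**What the plan says.** All references are to the combined protocol and SAP.

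- **The rule.** Section 4.4 excludes a person for "Having meditated in the 6 months preceding the experiment". It adds that exclusions rest on self-report at screening, without naming a screening stage.
- **Where the experiment begins.** Section 5.4: "The Qualtrics link contains the written informed consent form and the actual experiment".
- **Where meditation is asked.** Section 5.4 describes an initial online form on points "such as English proficiency, age, meditation experience, vision and hearing capabilities". Section 6 describes the same first stage and also lists meditation experience there, before the Qualtrics link is sent.
- **The wait.** Section 5.4: "If eligible, participants will be informed that the study will begin within three weeks". A cohort is released when its twentieth member is recruited or when three weeks are up. At that point "the coordinator will notify the cohort, instructing them to start the study within two days".
- **The Day 1 check.** After consent, "participants will proceed to the second screening, which involves answering additional questions about their use of concomitant medication". Those who pass are then asked about neurological or psychiatric illness, and failure at any step ends the survey automatically. Section 6 describes the same two topics and no others.
- **Randomisation.** Section 5.4 has Qualtrics allocate the arm after this screening and after the baseline measures.

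**The concern.** The exclusion window and the question that enforces it end on different days. The window closes when the experiment starts, and the question is answered when the person signs up. The days between are inside the window and are never asked about.

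Two things depend on this. The first is the sham. Section 5.2.2 says it is built to pass as meditation for newcomers and to create the expectation of real practice in people unfamiliar with it. Recent practice could make a track without an attentional anchor easier to recognise, which would weaken blinding. The second is the contrast. The intervention is three 10-minute sessions, so practice that participants in either arm bring with them narrows the difference in exposure between the arms.

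The data would not reveal the problem. None of the baseline items listed in Sections 5.3 and 5.4 (neuroticism, resilience, FFMQ, demographics, STAI-6, EMA, HRV) records recent meditation. The team could not identify the people concerned or run a sensitivity analysis without them.

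**Working it through.** The plan states no figure for the gap, so there is none to reproduce. It can be built from the plan's own timings.

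**Inputs**
- Longest cohort wait: three weeks (Section 5.4).
- Time allowed to start after notice: two days (Section 5.4).
- Length of the exclusion window: six months (Section 4.4), taken as 365 / 2 = 182.5 days.

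**Longest unchecked interval**
- 3 × 7 + 2 = 21 + 2 = 23 days.
- If the three weeks are counted from the coordinator's confirmation and not from submission of the form, the daily review can add about one day: 23 + 1 = 24.
- The figure is reached only by someone who signs up at the start of a cohort that does not fill early and who uses both days. Later recruits, and members of a cohort that fills early, wait less.

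**Share of the window**
- 23 / 182.5 = 12.6%, so at least 87.4% of the window is covered even at the maximum.

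**Coverage of the time-dependent exclusions**

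| Exclusion in Section 4.4 | Initial form (Sections 5.4 and 6) | Day 1 second screening |
|---|---|---|
| Recent or current neurological or psychiatric disease | not listed | asked |
| Psychoactive medication, current or in the past week | not listed | asked |
| Meditation in the past six months | asked | not asked |

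Three of the four exclusions depend on time. Meditation is the only one of the three not asked on the day the experiment starts.

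**Effect of the fix**
- With the question repeated on Day 1, the interval falls from at most 23 days to about zero, because the check and the start fall in the same session. The planned 60 participants do not change.

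**The case against.** The strongest reply is that the gap is small and its effect unproven.

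- **No evidence that anyone would breach the rule.** A reader might infer that excluded people will be randomised. The documents show only that such people would not be asked again. They give no rate of taking up meditation during the wait, and the text of the recruitment description mentioned in Section 4.2 is not shown, so it cannot be said to prompt practice. This objection stands.
- **The rule does not demand novices.** Section 4.4 bars only the last six months. A person with years of practice who stopped seven months ago is eligible, and may recognise the sham more readily than someone who has tried a few sessions. Closing the gap would not by itself secure the newcomers that Section 5.2.2 has in mind. This stands, and it limits the benefit of the fix.
- **Neither arm is favoured.** Any such practice comes before randomisation and so falls in either arm by chance. This stands.
- **Blinding is measured.** Section 5.3 collects an arm guess with confidence, an expectancy rating and the PARH, and Section 8.2 plans to analyse credibility and awareness of the hypothesis. This stands in part: more arm-guessing would be seen, but recent practice could not be identified as the cause.
- **The staging is deliberate.** Non-sensitive items come first and health items follow consent. That explains why meditation is on the first form. It does not explain leaving it off the second, since Section 5.4 already treats the first result as preliminary.
- **Screening might include a second check.** Section 4.4 names no stage, but the second screening is described in Sections 5.4 and 6, and neither mentions meditation.

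**Conclusion.** The mismatch is in the text. The procedure does not enforce the criterion as written for an interval of at most 23 days, 12.6% of the window. Anyone who began meditating in that interval would be randomised undetected.

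Two stronger readings are not supported. One would multiply an assumed take-up rate by 60 to give a number of ineligible participants; no such rate is in the documents, and the true number may be zero. The other would treat the gap as a source of bias between the arms; the timing relative to randomisation rules out a systematic difference at entry. What remains is slight dilution and somewhat weaker blinding, both of unknown size.

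The conclusion assumes that participants keep to the two-day instruction and that the second screening contains what Sections 5.4 and 6 describe. Priority: minor. It is worth making because it costs almost nothing and brings the procedure into line with the stated rule.

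**What to change.** Repeat the meditation question in the existing Qualtrics second screening on Day 1, before the baseline questionnaires and randomisation. Word it so that the six months end that day. Apply the automatic termination already used for the other second-screening questions, and amend the descriptions in Sections 5.4 and 6 to match Section 4.4.

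The cost is one yes/no item. There will be an occasional screen failure before randomisation, which can already happen at this stage for medication or illness. Some people who have waited for their cohort, with compensation pending, may also falsely deny recent practice, so the item will reduce the gap without guaranteeing its closure.

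A message asking people not to start meditating while they wait is not recommended. It could signal the study's focus before baseline in a trial designed to separate genuine effects from demand effects.

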4.5. Participant discontinuation criteria

The participant has the right to withdraw from the trial at any time without facing any negative consequences.

5. STUDY DESIGN, PROCEDURES AND METHODOLOGY

5.1 Study design

The research will adhere to a randomized, double-blind, 2-arm parallel-groups design. Participants will engage remotely from their home. The entire study duration is set at 3 days.

5.2 Intervention

Participants will be randomly allocated into one of two arms. Participants of the experimental group will listen for three consecutive days to a 10-minute mindfulness track once a day (experimental condition). Participants of the control group will listen for three consecutive days to a 'sham meditation' track once a day (control condition). The 'sham meditation condition' is an audio track that mimics the structure or elements of a meditation session but lack the authentic content or efficacy associated with genuine meditation practices.

5.2.1. Features of the mindfulness intervention (experimental condition)

The mindfulness intervention is comprised of three tracks of mindfulness practice adapted from a traditional Mindfulness-Based Stress Reduction (MBSR) protocol. The three mindfulness tracks incorporate essential elements of the mindfulness practice: a) Cultivating attentional stability by directing focus to present-moment bodily experiences (Moore et al., 2012), and b) fostering mindful meta-awareness by nonreactivity and nonjudgmentally observing and accepting experiences (Dahl et al., 2015). These components are closely associated with successful mindfulness training and effective stress regulation according to a systematic review of Stein et al., 2020 that investigated the efficacy of different mindfulness components. See Appendix A to find the script of tracks that will be used in the current experiment. To enhance the protocol's validity, we conducted a focus group comprising 5 certified international mindfulness instructors. Their insights informed decisions on the duration, frequency, and content of the mindfulness tracks. Notably, one instructor that participated in the focus group recorded the audio tracks that will be used in the current study.

